Both an interim and an end of study analysis for the primary effectiveness endpoint are planned. The primary effectiveness endpoint is the difference between the EBV treatment arm and control arm in percentage of study participants who reach a threshold of $\geq 15\%$ improved FEV₁, collected post-bronchodilator, at 1 year (see Table 1). The FEV₁ value will be calculated by determining the percentage change for FEV₁ from baseline to 1-year post-procedure using: $((\text{FEV}_1 \text{ at 1 year follow-up} - \text{FEV}_1 \text{ at baseline}) / \text{FEV}_1 \text{ at baseline})$ for individual study participants. The two arms will be compared using the standard normal Z-statistic.

Table 1. Primary Effectiveness Endpoint

Variable	Unit	Values Statistically Evaluated
Forced Expiratory Volume (FEV ₁)	$\geq 15\%$ improved	percentage of participants

An interim data analysis designed to evaluate effectiveness for continuing crossover of control arm study participants at the 1 year follow-up to EBV treatment will be performed

when 74 (50% of the total 147) study participants have completed the 1 year follow-up. The interim analysis will be reviewed by the DSMB.

To account for the interim analysis, the power spending function, defined as:

$$\alpha(t) = \alpha t^\phi$$

will be used to preserve an overall type I error rate of 0.05 for the study. Using the nTerim program (Statistical Solutions) to calculate the power spending function with:

$$\alpha = .05, \phi = 2.3 \text{ and } t = .5, \alpha(t) = .01,$$

the value of the Z-statistic must exceed 2.571 (nominal alpha <0.01) for the null hypothesis to be rejected at this interim look (see Table 2).

Table 2. Power Spending Function for Interim Analysis

Looks	1	2
Time	0.5	1
Lower Bound	-2.57057	-2.00360
Upper Bound	2.57057	2.00360
Nominal Alpha	0.01015	0.04511
Incremental Alpha	0.01015	0.03985
Cumulative Alpha	0.01015	0.0500
Exit Probability	38.75	50.52
Cumulative Exit Probability	38.75	89.28

If $Z \geq 2.571$ then continuing crossover of control arm study participants will be strongly justified since the p-value will be ≤ 0.01 . This observation may provide evidence to stop the trial early.

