 - i. Persistence of the treatment effect will be evaluated by determining the difference between study arms for ‘absolute change from baseline’ for FEV₁ at 45 days, 6 months, and 1 year. The FEV₁ value will be calculated using: ((FEV₁ at each of the follow-up time points) subtracted from (FEV₁ at baseline)) for individual study participants to determine the mean absolute change for each study arm. At each of the three time points, descriptive statistics will include means, standard deviations and 95% confidence intervals. A two-sample t-statistic will be used to quantify the magnitude of the difference between study groups. A repeated-measures model (GEE with an identity link function and exchangeable correlation structure) will be used to model the entire time course of outcomes as a function of baseline value and a main effect indicating treatment group membership.
 - ii. Persistence of the treatment effect will be evaluated by determining the difference between study arms for ‘percentage change from baseline’ for FEV₁ at 45 days, 6 months, and 1 year. The FEV₁ values will be calculated using: ((FEV₁ at each of the follow-up times) subtracted from (FEV₁ at baseline divided by FEV₁ at baseline)) for individual study participants to determine the mean absolute change for each study arm. At each of the three time points, descriptive statistics will include means, standard deviations and 95% confidence intervals. A two-sample t-statistic will be used to quantify the magnitude of the difference between study groups. A repeated-measures model (GEE with an identity link function and exchangeable correlation structure) will be used to model the entire time course of outcomes as a function of baseline value and a main effect indicating treatment group membership.
- d. 6-Minute Walk Distance (6MWD)
 - i. Difference between study arms in ‘absolute change from baseline’ for 6MWD at 1 year. Descriptive statistics will include means, standard deviations and 95% confidence intervals. A two sample t-statistic will be used to quantify the magnitude of the difference between study groups.
 - ii. Difference between study arms in ‘percentage change from baseline’ for 6MWD at 1 year. Descriptive statistics will include means, standard deviations and 95% confidence intervals. A two sample t-statistic will be used to quantify the magnitude of the difference between study groups.
- e. The secondary effectiveness endpoints are summarized in Table 3.

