Table 3. Secondary Effectiveness Endpoints

Variable	Unit	Values Statistically Assessed
Target Lobe Volume Reduction (TLVR)	milliliters	mean absolute change
TLVR	percent	mean percent change
SGRQ Global Score	Points	mean absolute change
SGRQ	percent	mean percent change
FEV ₁	Liters	mean absolute change
FEV ₁	percent	mean percent change
6-Minute Walk Distance	Meters	mean absolute change

6MWD	percent	mean percent change
------	---------	---------------------

C. Analysis of Additional Effectiveness Endpoints

a. Supporting Evidence for Effectiveness

The following additional effectiveness endpoints will be measured for both study arms. These are expected to provide supporting evidence of the effectiveness of EBV treatment. Results will be described with summary statistics. These endpoints will be described for each study arm separately and comparatively between arms by calculating mean change or difference in proportions, whichever is appropriate for the variable being analyzed. The definitions for these additional effectiveness endpoints are shown in Table 4.

Table 4. Additional Effectiveness Endpoints

Spirometry Measures		
FEV ₁	≥12% improved	Percentage of participants
Forced Vital Capacity (FVC)	liters	mean absolute and percent change
FEV ₁ /FVC	ratio	mean absolute change
DL _{co}	percentage	mean absolute and percent change
Body Plethysmography Measures		
Residual Volume (RV)	liters	mean absolute and percent change
Inspiratory Capacity (IC)	liters	mean absolute and percent change
Functional Residual Capacity (FRC)		mean absolute and percent change
Total Lung Capacity (TLC)	liters	mean absolute and percent change
RV/TLC	ratio	mean absolute change
IC/TLC	ratio	mean absolute change
Patient-Reported Health Status Measures		
SGRQ Global Score	≥4 points improved	percentage of participants
	≥8 points improved	percentage of participants
SGRQ Domain Scores		
‘Symptoms’	points	mean absolute change
‘Activity’	points	mean absolute change
‘Impacts Daily Life’	points	mean absolute change
mMRC Score	semi-quantitative scale score	mean absolute change
COPD Assessment Test (CAT)	points	mean absolute change
Transitional Dyspnea Index (TDI)	points	mean absolute change
	≤1 point improved	percent of participants
Short Form (SF)-36 Health Survey	points	mean absolute change
EQ-5D Health Survey	points	mean absolute change
Other Measures		
BODE Index	semi-quantitative scale score	mean absolute change

	≤1, 0, ≥1 change	percentage of participants

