Pulmonx Corporation

Clinical Investigational Plan #630-0012_H

Statistical Analysis Plan – Revised 26 October 2017 (supersedes Appendix 19 from CIP #630-0012_H)

Change History:

SAP Section	Change	Rationale
Study Design	Update the enrolled study participants to 190.	To reflect the number of study participants enrolled in the study.
Secondary Effectiveness Endpoints	Analyses of secondary endpoints were updated to limit the number of statistical comparisons. Now limited to Absolute Change in FEV1, 6MWD, and SGRQ score. The use of Hochberg method was specified to address multiplicity.	To control the family-wise Type I error for the secondary endpoints, analyses of secondary endpoints were limited.
Safety Endpoint	Deleted "of the EBV treatment arm".	To reflect that adverse events will be compared between treatment arms during the short-term and long-term periods.
Additional Measures	Additional measures were updated, specifically, Treatment Lobe Volume Reduction (TLVR) for the treatment arm only was moved from Secondary to Additional.	Moved to "Additional Measures" since this parameter indicates the mechanism of action and unable to compare to a Control group as no TLVR is expected without an intervention.
Statistical Methods – I	Confidence intervals were removed from adverse event reporting. In place of presenting confidence intervals, adverse event rates for those events occurring in at least 3% of subjects in either group will be compared using a Fisher's Exact test.	Making adverse event reporting consistent with typical way of presenting and analyzing adverse events.
Statistical Methods II (C)	Pseudo-sites clarified to be created from sites within the same country.	Clarification.
Statistical Methods III	Definitions of populations clarified.	Clarification.
Statistical Methods IV	Update to "three" secondary effectiveness variables in the text and in Table 3.	To reflect the modified secondary effectiveness endpoints.
Statistical Methods IV (B)	Update to analyses of secondary endpoints, including use of Hochberg method.	To control the family-wise Type I error for the secondary endpoints,

		analyses of secondary endpoints were limited.
Statistical Methods IV (C)	Update to analyses of additional effectiveness endpoints.	As a result of modifying the secondary effectiveness endpoints, additional measures were also updated.

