Statistical Methods V	Clarify that covariate analyses are to be performed on primary and secondary endpoints only. Removed variables that will not have data available for control subjects.	Clarification.
	Deleted "Follow-up" column as no "Follow-up" variables will be used in covariate analysis.	
Safety Analyses VII	Updated to include Control arm in summary of adverse events and specify Fisher's Exact tests of events occurring in at least 3% of either treatment arm.	In place of presenting confidence intervals, adverse event rates for those events occurring in at least 3% of subjects will be compared using a Fisher's Exact test.
Statistical Methods IX	Included imputation strategy for subject deaths and clarified secondary endpoints would utilize same imputation method as primary endpoint.	Subject death prior to endpoint visit should be considered a failure. Secondary endpoints should account for missing data.
Statistical Methods X	Clarification to statistical tests.	Clarification.
Other	Tables and text formatted.	Ease of reading.

Analysis Summary

Study Title: Lung Function Improvement after Bronchoscopic Lung Volume Reduction with Pulmonx Endobronchial Valves used in Treatment of Emphysema (Clinical Protocol 630-0012).

Patient Population: Male and female patients with severe heterogeneous emphysema meeting the study eligibility criteria.

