Study Design: This will be a multi-center, prospective, randomized, controlled study with EBV treatment statistically evaluated using Intent-to-Treat (ITT) analyses. A maximum of 183 ITT study participants, who meet study entry criteria, consisting of screening eligibility criteria, baseline eligibility criteria, and procedure eligibility criteria, were planned to be enrolled. A total of 190 study participants were enrolled. Safety and effectiveness of bronchoscopic lung volume reduction (BLVR) using the Pulmonx EBV will be evaluated at 1 year. An interim analysis designed to evaluate effectiveness for continuing crossover of control participants at 1 year to EBV treatment will be performed when 74 study participants have completed the 1-year follow-up. For study participants who have been treated with EBV, a secondary valve intervention such as valve removal, replacement, or adjustment may be considered during the study follow-up. Long-term data will be collected annually for EBV-treated study participants through 5 years. Per the regulatory plan agreed to with FDA, 1-year of follow-up is required pre-approval and the remaining 4 years of follow-up will be conducted post-approval.

Primary Effectiveness Endpoint

The percentage of study participants in the Endobronchial Valve (EBV) treatment arm who meet the threshold of \geq 15% improved forced expiratory volume in one second (FEV₁) as compared to the control arm at 1 year. Improved FEV₁ will be calculated by determining the percentage change for FEV₁ from baseline to 1-year post-procedure for individual study participants.

Secondary Effectiveness Endpoints

- 1) FEV₁: Difference between study arms in 'absolute change from baseline' for FEV1 at 1 year.
- 2) 6-Minute Walk Distance (6MWD): Difference between study arms in 'absolute change from baseline' for 6MWD at 1 year.
- 3) St. George's Respiratory Questionnaire: Difference between study arms in 'absolute change from baseline' for SGRQ score at 1 year.

Safety Endpoint

Evaluation of the short- and long-term adverse events profile during the treatment period, defined as the day of the study procedure until 45 days after the study procedure (short), and in the post-treatment period, defined as 46 days after the study procedure until the 1-year followup visit (long).

Additional Measures

- Treatment Lobe Volume Reduction (TLVR) for the treatment arm only
- Spirometry, including FEV₁, forced vital capacity (FVC) and the ratio of FEV₁/FVC

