- Body plethysmography, including residual volume (RV), inspiratory capacity (IC), functional residual capacity (FRC), TLC, and the ratios of RV/TLC and IC/TLC
- SGRQ Total and domain (i.e. 'symptoms', 'activity' and 'impacts on daily life') scores
- Modified Medical Research Council (mMRC) Dyspnea Scale Score
- BODE Index
- Transitional Dyspnea Index (TDI) from Baseline Dyspnea Index (BDI)
- COPD Assessment Test (CAT)
- SF-36 Health Survey score
- EQ-5D Health Survey score
- Health Care Utilization Questionnaire
- 6MWD test
- Borg scale dyspnea scores before and after 6MWD test
- Change in use of 'maintenance' medications, including bronchodilators, corticosteroids, antibiotics, and anti-inflammatories
- Pulmonary rehabilitation compliance diary responses
- EXACT-PRO diary responses
- Health status change responses
- Carbon Monoxide Diffusing Capacity (DL_{CO})
- Lung radiographic features

Interim Analysis

An interim data analysis designed to evaluate effectiveness for continuing crossover of control arm study participants at 1-year to EBV treatment will be performed when 74 (50% of the total 147) study participants have completed the 1-year follow-up. The interim analysis will be reviewed by the DSMB and FDA. If crossover of control arm study participants is found to be justified by the interim analysis, then crossover of control arm study participants may be continued. If the DSMB recommends not continuing crossing control arm participants to EBV treatment, then those control arm patients who have not yet crossed over will exit from the study per protocol after the 1-year visit.

Long-Term Follow-up

Data will be collected annually through 5 years. Per the regulatory plan agreed to with FDA, 1 year of follow-up is required pre-approval and the remaining 4 years will be conducted post-approval. The 2-, 3-, 4-, and 5-year data will consist of FEV₁ and adverse events.

Definition of Study Success: The study will be a success if the difference between the EBV Treatment arm and Control arm for the percentage of study participants meeting the threshold of \geq 15% improved in FEV₁ differs significantly (two-sided test at p<0.05) in favor of the treatment group at 1 year. This evaluation will be conducted at 1-year post-randomization.

Number of Study Participants: 190

Statistical Methods

I. Descriptive Statistics

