A. Analysis of the Primary Effectiveness Endpoint

Both an interim and an end of study analysis for the primary effectiveness endpoint are planned. The primary effectiveness endpoint is the difference between the EBV treatment arm and control arm in percentage of study participants who reach a threshold of \geq 15% improved FEV₁, collected post-bronchodilator, at 1 year (see Table 1). The FEV₁ value will be calculated by determining the percentage change for FEV₁ from baseline to 1-year post-procedure using: ((FEV₁ at 1-year follow-up subtracted from FEV₁ at baseline) / (FEV₁ at baseline)) for individual study participants. The two arms will be compared using the standard normal Z-statistic.

Table 1. Primary Effectiveness Endpoint

Variable	Unit	Values Statistically Evaluated
Forced Expiratory Volume (FEV ₁)	>15% improved	percentage of participants

An interim data analysis designed to evaluate effectiveness for continuing crossover of control arm study participants at the 1-year follow-up to EBV treatment will be performed when 74 (50% of the total 147) study participants have completed the 1-year follow-up. The interim analysis will be reviewed by the DSMB.

To account for the interim analysis, the power spending function, defined as:

$$\alpha(t) = \alpha t^{\phi}$$

will be used to preserve an overall type I error rate of 0.05 for the study. Using the nTerim program (Statistical Solutions) to calculate the power spending function with: $\alpha = .05, \phi = 2.3 \text{ and } t = .5, \alpha(t) = .01,$

the value of the Z-statistic must exceed 2.571 (nominal alpha <0.01) for the null hypothesis to be rejected at this interim look (see Table 2).

 Table 2. Power Spending Function for Interim Analysis

Looks	1	2
Time	0.5	1
Lower Bound	-2.57057	-2.00360
Upper Bound	2.57057	2.00360
Nominal Alpha	0.01015	0.04511
Incremental Alpha	0.01015	0.03985
Cumulative Alpha	0.01015	0.0500
Exit Probability	38.75	50.52
Cumulative Exit Probability	38.75	89.28

If Z \geq 2.571 then continuing crossover of control arm study participants will be strongly justified since the p-value will be \leq 0.01. This observation may provide evidence to stop the trial early.

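### The SAP's only explicit formula for the primary endpoint has its sign reversed: read literally, an FEV1 loss of 15% or more counts as a response

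*SAP*

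**What the plan says.** The SAP of 26 October 2017 declares in its header that it "supersedes Appendix 19 from CIP #630-0012_H", so it is the controlling analysis text.

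- **SAP IV.A (primary analysis).** The endpoint is the proportion of participants with FEV1 improved by at least 15% at 1 year. The individual value is computed from "FEV₁ at 1-year follow-up subtracted from FEV₁ at baseline", divided by FEV1 at baseline.
- **SAP, Primary Effectiveness Endpoint (summary).** "Improved FEV₁ will be calculated by determining the percentage change for FEV₁ from baseline to 1-year post-procedure for individual study participants".
- **SAP, Definition of Study Success.** The arms must differ significantly "in favor of the treatment group at 1 year".
- **Protocol Appendix 19, IV.A (superseded).** The same formula appears in symbols and in the other order: 1-year value minus baseline, over baseline.
- **Protocol Appendix 19, IV.B.c (superseded).** The secondary FEV1 changes already used the reversed phrase: follow-up "subtracted from (FEV₁ at baseline".
- **SAP change history.** No change to IV.A is listed. The nearest entry is the general one, "Tables and text formatted".

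**The concern.** Subtracting A from B gives B − A. The SAP's phrase therefore yields a quantity that is positive when lung function declines, and the 15% threshold is applied to that quantity. The formula is in words, so a minus sign lost in the PDF cannot explain it.

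Responder status supplies the two proportions in the Z-statistic, which is compared with 2.571 at the interim look and 2.004 at the end. A SAP is also a programming specification, and independent validation checks code against it. Code that follows the formula gets the wrong direction. Code that ignores it departs from the only explicit primary formula in the controlling text.

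**Working it through.** **1. The plan's own figures.** Inputs from protocol 20.3.1: 35% vs 10%, two-sided alpha 0.05, 90% power, 2:1 allocation. With Δ = 0.25, r = 2 and p̄ = (0.10 + 2 × 0.35)/3 = 0.2667:

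- Uncorrected control-arm n = [1.960 × √(1.5 × 0.2667 × 0.7333) + 1.282 × √(0.10 × 0.90 + 0.35 × 0.65/2)]² / 0.25² = (1.0615 + 0.5785)² / 0.0625 = 43.03.
- With continuity correction, n = (43.03/4) × [1 + √(1 + 6/(2 × 43.03 × 0.25))]² = 48.8, rounded up to 49. The total is 49 + 98 = **147**, as stated.
- Spending 0.05 × 0.5^2.3 = 0.01015 at the interim gives boundaries of 2.5706 and 2.0036, as stated.

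These figures take responders to be improvers, so correcting the sign changes none of them.

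**2. The formula on example values.** The baseline of 0.80 L is illustrative.

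| FEV1 at 1 year | (1 year − baseline)/baseline | Responder | SAP wording: (baseline − 1 year)/baseline | Responder |
|---|---|---|---|---|
| 0.92 L | 0.12/0.80 = +15% | yes | −0.12/0.80 = −15% | no |
| 0.68 L | −0.12/0.80 = −15% | no | 0.12/0.80 = +15% | yes |

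**3. The planned test statistic.** Enrolment is 190. A 2:1 split is taken as 127/63, all evaluable (assumptions). The pooled rate is (127 × 0.35 + 63 × 0.10)/190 = 0.2671, so

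Z = 0.25 / √(0.2671 × 0.7329 × (1/127 + 1/63)) = 0.25/0.0682 = **+3.67**.

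**4. The same trial coded literally.** The documents give no SD for percentage change in FEV1. Assume normal changes with a common SD. Set each arm's mean so that P(change ≥ 15) equals the design rate:

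- EBV mean = 15 − 0.3853 × SD
- control mean = 15 − 1.2816 × SD

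A literal responder then has change ≤ −15.

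| SD (points) | Mean EBV / control | Literal rate EBV / control | Z |
|---|---|---|---|
| 10 | 11.1 / 2.2 | 0.4% / 4.3% | −1.92 |
| 12 | 10.4 / −0.4 | 1.7% / 11.2% | −2.85 |
| 15 | 9.2 / −4.2 | 5.3% / 23.6% | −3.74 |
| 20 | 7.3 / −10.6 | 13.2% / 41.4% | −4.36 |
| 25 | 5.4 / −17.0 | 20.8% / 53.2% | −4.54 |
| 30 | 3.4 / −23.4 | 26.9% / 61.1% | −4.56 |

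With 98/49 patients instead of 127/63, the correct Z is +3.23, and literal coding gives −3.29 to −3.99 for SD 15 to 25.

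**5. Lesser points.** All concern endpoints reported with summary statistics, outside the primary and Hochberg-controlled tests.

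- *TDI responder.* Appendix 19 Table 4 has "≤1 point improved", and SAP Table 4 carries it over. Protocol 13.2.3 treats a change of 1 unit or more as meaningful. Three domains scored −3 to +3 give a total of −9 to +9. Taken as an inequality alone, the rule admits −9 to +1. If the word improved is allowed to exclude deteriorations, it still excludes gains of 2 or more. Among whole-number scores, only +1 meets both rules.
- *BODE change classes.* Table 4 prints classes of at most 1, 0, and at least 1, which overlap. A lost minus sign is possible, so this is a query only.
- *mMRC.* Protocol 13.2.2 grades it 1 to 5. The BODE table in 13.12 gives points for 0 to 4, so an unconverted grade 5 has no BODE points.

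**The case against.** The strongest reply is that nobody would be misled. IV.A says improved, the same sentence speaks of change from baseline to 1 year, and the summary and success definition agree. Protocol 7.1 and 20.3, which the SAP does not supersede, also say improved. This stands as to intent, and it is why the defect is a wording error and not an undefined endpoint. It does not make the formula right, and nothing else in the SAP restates it correctly.

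Second, under the design assumptions literal coding produces a negative Z. That would be a conspicuous failure with control apparently better, not a false claim of effectiveness, and it would probably be noticed. This also stands and limits the practical risk.

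Third, the size in step 4 rests on assumed SDs, normality and full evaluability. At SD 10 the reversed Z is only −1.92, and SDs of 20 to 30 force control means of about −11% to −23%, which nothing in the documents supports. This too stands: the table is illustrative. The sign is negative in every row, and the 0.80 L example needs none of these assumptions.

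Finally, the TDI, BODE and mMRC items are separate matters of low consequence. A constant offset in mMRC grade leaves its change scores unaffected. The main point does not depend on any of them.

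**Conclusion.** The concern holds. The SAP's sole explicit formula for the primary FEV1 change is reversed and contradicts the endpoint it is meant to implement. Followed literally, it would turn a planned Z of +3.67 into a negative value: −3.74 to −4.56 for an assumed SD of 15 to 30 points, smaller in size for lower SDs. The reversal of each patient's sign follows from the wording alone; the Z values depend on the stated assumptions. Harm arises only if the phrase is programmed as written. The unlisted change from the Appendix 19 formula suggests an inadvertent slip. It should be corrected in the SAP, and it casts no doubt on the sample size, boundaries or error control.

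**What to change.** In SAP IV.A, replace the worded calculation with (FEV1 at 1 year − FEV1 at baseline)/FEV1 at baseline, with a responder defined as a value of 0.15 or more. Record the correction in the change history. The cost is one phrase, with no change to design or data.

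At the same revision:

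- change the TDI responder in SAP Table 4 to a gain of at least 1 point, to match protocol 13.2.3;
- confirm whether the BODE change classes should read at most −1, 0, and at least 1;
- check the mMRC case report form against protocol 13.2.2 and 13.12, and score BODE on grade minus 1 only if the form records 1 to 5.

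These need one or two symbols in Table 4 and one check of the form.

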The study hypothesis will be tested again at the end of the study. The Z-statistic will be calculated again, and by taking into account the interim analysis, will have a final critical boundary value of 2.004, per the nTerim program. If the trial is not stopped as a result of the interim analysis, then the final Z-statistic must be greater than or equal to 2.004 in order to reject the null hypothesis at the final analysis (at the overall 2-sided 5% significance level). Test statistic is "Z" as defined as:

$$Z = \frac{p_T - p_C}{\sqrt{p(1 - p)\left(\frac{1}{n_T} + \frac{1}{n_C}\right)}}$$

Where,

 p_T and p_C are the proportions of success for the primary endpoint in the treatment and control groups, respectively, *p* is the pooled estimate of the success rate, and

 n_T and n_C are the sample sizes obtained in the treatment and control groups,

respectively. Two sets of (p, p_T , p_C , n_T , n_C) will be obtained: one at the interim analysis and one at end of the study.

B. Analysis of the Secondary Effectiveness Endpoints

The following describes the analysis techniques to be used for each of the secondary endpoints. To control the family-wise type I error rate at 5%, the Hochberg step-up procedure will be utilized (Hochberg, 1988).

a. FEV₁

Difference between study arms in 'absolute change from baseline' for FEV1 score at 1 year. Descriptive statistics will include means, standard deviations and 95% confidence intervals. An analysis of covariance (ANCOVA) with factor of treatment and baseline FEV1 as a covariate will be used to test the difference between treatment arms. P-value will be adjusted for multiple imputation.

b. 6-Minute Walk Distance (6MWD)

Difference between study arms in 'absolute change from baseline' for 6MWD at 1 year. Descriptive statistics will include means, standard deviations and 95% confidence intervals. An analysis of covariance (ANCOVA) with factor of treatment and baseline 6MWD as a covariate will be used to test the difference between treatment arms. P-value will be adjusted for multiple imputation.

c. St. George's Respiratory Questionnaire (SGRQ)

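### The interim and final boundaries (2.571 and 2.004) were computed for 74 of 147 participants and not recomputed for the 190 enrolled; the effect on the error rate is small

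*SAP*

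**What the plan says.** SAP section IV.A plans one interim and one final test of the primary endpoint, the proportion with at least 15% improvement in FEV1 at 1 year. The interim is to be "performed when 74 (50% of the total 147) study participants have completed the 1-year follow-up". The spending function is alpha(t) = 0.05 × t^2.3, entered at t = 0.5. It "will be used to preserve an overall type I error rate of 0.05 for the study".

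Table 2 gives boundaries of 2.57057 and 2.00360. At the interim, "the value of the Z-statistic must exceed 2.571 (nominal alpha <0.01) for the null hypothesis to be rejected at this interim look", and the SAP adds that crossing this value could be grounds for ending the trial early. The end-of-study test "will have a final critical boundary value of 2.004, per the nTerim program", and it is described as being "at the overall 2-sided 5% significance level".

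Elsewhere the revised SAP updates the sample size. Under Study Design: "A total of 190 study participants were enrolled". The Number of Study Participants entry is also 190. Section III.B defines the primary population as all randomised patients, and section IX imputes missing 1-year values, so all 190 enter the final Z-statistic. The change history lists the update to 190 but no change to the interim design. No section gives a rule for recomputing t or the boundaries.

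**The concern.** A spending function fixes how much alpha may be used at a given information fraction. The final boundary then depends on that fraction through the correlation between the interim and final statistics. Here the denominator of the fraction grew from 147 to 190 and the boundaries stayed the same.

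Two things follow. The printed interim value is more lenient than the SAP's own function allows at 74/190. And once 2.571 is applied at the interim, a final value of 2.004 is slightly too small, because the two statistics are less correlated than was assumed. The final value is the threshold for success in a study meant to support a premarket approval application (Protocol section 4.0). A final Z between 2.004 and about 2.016 would be called significant under a 5% guarantee that, in normal theory, is not quite met.

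**Working it through.** **Inputs.** From SAP IV.A: two-sided alpha 0.05, exponent 2.3, interim at 74, boundaries 2.571 and 2.004. From SAP Study Design: 190 enrolled. From Protocol section 20.3.1: planned enrolment 183, 20% allowance for loss and incomplete data, responder rates 35% and 10%. The documents do not give the number analysed at the interim, so 74 is taken as planned.

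**Method.** The interim boundary c1 solves 2 × [1 − Φ(c1)] = alpha(t). The final boundary c2 solves P(|Z1| < c1 and |Z2| ≥ c2) = 0.05 − alpha(t), where Z1 and Z2 are standard bivariate normal with correlation √t.

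**Reproducing Table 2.** At t = 0.5, alpha(t) = 0.05 × 0.5^2.3 = 0.01015, c1 = 2.5706 and c2 = 2.0036. The final nominal alpha is 0.0451 and the total error 5.00%. This matches Table 2, so the method is identified. (74/147 is 0.503; that rounding is immaterial.)

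**The same calculation at other final numbers.** The last two columns use the printed 2.571 at the interim.

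| Final N | t = 74/N | alpha(t) | Function's c1 / c2 | Overall error of 2.571 / 2.004 | c2 that restores 5% after 2.571 |
|---|---|---|---|---|---|
| 152 | 0.487 | 0.0096 | 2.592 / 2.001 | 5.01% | 2.005 |
| 171 | 0.433 | 0.0073 | 2.684 / 1.993 | 5.07% | 2.011 |
| 183 | 0.404 | 0.0062 | 2.735 / 1.989 | 5.10% | 2.014 |
| 190 | 0.389 | 0.0057 | 2.764 / 1.987 | 5.12% | 2.016 (2.0155) |

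The rows for 171 and 152 assume that 10% and 20% of the 190 contribute no information (190 × 0.9 = 171; 190 × 0.8 = 152). The row for 183 shows that an ITT analysis of the planned enrolment already had the mismatch.

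**Exact check.** The normal approximation is not the last word for a binary endpoint. I enumerated the binomial outcomes with the SAP's pooled Z, assuming 49/25 at the interim and 127/63 at the end, with boundaries 2.571 and 2.004.

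| Common responder rate | Overall two-sided error |
|---|---|
| 5% | 4.44% |
| 10% | 4.88% |
| 15% | 5.04% |
| 20% | 5.09% |
| 25% | 5.09% |
| 30% | 5.11% |

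The part of this error that favours treatment runs from 1.55% to 2.39%. With 2.016 as the final value, the overall error is still 4.88% at a rate of 10%, and 5.08% at 30%.

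**The case against.** **The interim governs only crossover.** That is its stated purpose (Protocol sections 7.6 and 20.7). If it could never reject the null, the final test at 2.004 alone would have an error of 4.51%, which is conservative. But SAP IV.A does provide for rejection at that look and for possible early stopping, so its alpha must be counted.

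**Headcount is not information.** Imputed values add less than observed ones. If the design's 20% allowance applies to the 190, about 152 are informative and the error is 5.01%. This stands: 5.12% is the upper end of a range that the documents do not narrow.

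**The final value is not simply too lenient.** The SAP's function at 74/190 gives 1.987, so 2.004 is stricter than that. It is too small only after an interim judged at 2.571. This also stands, and it is why the correction depends on what was done at the interim.

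**Stronger readings.** A reader might infer that the 5% guarantee has materially failed. The exact results do not support that: the error is below 5% at the protocol's 10% control rate, and the false-positive rate in favour of treatment stays under 2.5% at every rate examined. A reader might also infer that Table 2's exit probabilities are wrong, since exact power at 35% against 10% is 93.6% with 147 and 97.8% with 190, against 89.28% in the table. That does not follow. A drift set for 90% fixed-sample power gives 89.5% for these boundaries. The 147 includes a continuity correction (132 without it) that the Z-test does not use, and 190 simply brings more power.

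**Conclusion.** The point holds as a minor one. The printed boundaries belong to t = 0.5 and are not what the SAP's spending function gives for the trial that was enrolled. In normal theory the printed pair exceeds 5% by at most about 0.1 percentage point, and the excess almost vanishes if about 152 participants are informative. The mismatch was not created by enrolling 190; it was present for an ITT analysis of 183.

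The conclusion assumes that 74 were analysed at the interim, that 2.571 was or will be applied there, and that rejection at that look counts. The documents settle only the last of these. What remains is that the SAP fixes a decision threshold it cannot derive from its own method, and gives no rule for correcting it.

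**What to change.** Define t in SAP IV.A as the number actually analysed at the interim divided by the number in the final analysis, and say how participants with imputed outcomes count towards it. Then, before the final analysis:

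- If the interim was judged at 2.571, keep the alpha it spent (about 0.0101) and take the final boundary from the joint distribution at the actual t. This is about 2.016 at 74/190, or 2.011 at 74/171.
- If the interim has not been run, use the function's own values, 2.764 and 1.987 at 74/190.

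Update the boundary and alpha rows of Table 2 to match. The exit probabilities need no correction as errors; if they are kept, label them as belonging to the 90%-power design at t = 0.5.

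The cost is one rerun of the boundary program and a few changed figures. After a 2.571 interim, the final threshold becomes slightly stricter.
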